1. LIST OF ABBREVIATIONS

[figure not shown]
Abbreviation	Definition
AE	adverse event
AEM	adverse event monitoring
ANMAT	Administración Nacional de Medicamentos, Alimentos y Tecnología Médica
ANVISA	Agência Nacional de Vigilância Sanitária
CEISH	Ethics Committee of Human Research
CENDEISSS	Centro de Desarrollo Estratégico e Información en Salud y Seguridad Social
CI	confidence interval
COFEPRIS	Comisión Federal para la Protección contra Riesgos Sanitarios
COMBIOETICA	La Comisión Nacional de Bioética
CONEP	Comissão Nacional de Ética em Pesquisa
CONIS	Consejo Nacional de Investigación en Salud
CRF	case report form
DCF	data collection form
DCT	data collection tool
ECOG	Eastern Cooperative Oncology Group
eCRF	electronic case report form
ERB	ethical review board
GPP	Good Pharmacoepidemiology Practices
HR	hazard ratio
IEC	independent ethics committee
IMDC	International Metastatic Renal Cell Carcinoma Database Consortium
INVIMA	Instituto Nacional de Vigilância de Medicamentos y Alimentos
IRB	institutional review board
ISPE	International Society for Pharmacoepidemiology
ISPOR	International Society for Pharmacoeconomics and Outcomes Research
MSKCC	Memorial Sloan Kettering Cancer Center
NIS	noninterventional study
OQA	Office of Quality Assurance
PFS	progression-free survival
PI	principal investigator
Q	quarter
RAINBOW	RAolibizumab Compared With Laser Therapy for the Treatment of INFants BOrn Prematurely With Retinopathy of Prematurity

PFIZER CONFIDENTIAL

Abbreviation	Definition
RCC	renal cell carcinoma
RECIST	Response Evaluation Criteria in Solid Tumors
PPD	PPD
SAS	Statistical Analysis Software
STAR-TOR	Registry For Temsirolimus, Sunitinib, And Axitinib Treated Patients With Metastatic Renal Cell Carcinoma (mRCC), Mantle Cell Lymphoma (MCL), And Gastro-Intestinal Stroma Tumor (GIST)
TBD	to be determined

PFIZER CONFIDENTIAL

3. ABSTRACT

A Retrospective Medical Record Review of First-Line Sunitinib Administration Schedules and Outcomes Among Patients with Metastatic Renal Cell Carcinoma in Latin America

Version 1

Background: Over the past decade, targeted therapies have yielded significant improvement in the clinical outcomes of patients with metastatic renal cell carcinoma (RCC), leading to international guidelines for standard first-line treatment with sunitinib, bevacizumab + interferon, or pazopanib for patients with good or intermediate prognoses.¹ The standard administration schedule for sunitinib as first-line treatment for metastatic RCC is 50 mg per day for 4 weeks followed by 2 weeks off (ie, a 4/2 schedule). However, recent studies suggest that a schedule modified to 2 weeks of sunitinib followed by 1 week off (ie, a 2/1 schedule) improves tolerability with comparable outcomes.²⁻⁵ A change to the schedule may result in fewer Grade 3 or Grade 4 toxicities and increased treatment duration.⁵⁻⁹

Rationale: Despite the potential benefit from a modified treatment schedule evidenced in several studies among patients in the United States and Europe, real-world clinical outcomes among patients who have switched from the 4/2 to the 2/1 schedule for metastatic RCC in Latin America are unexplored. The current study will provide a description of demographic and clinical characteristics, sunitinib treatment patterns, and associated adverse events (AEs) and outcomes among adult patients in Latin America who were diagnosed with metastatic RCC and who received first-line sunitinib on the 4/2 schedule and then switched to the 2/1 schedule. In Brazil, feasibility assessments indicate many physicians start patients on the 2/1 schedule upon initiation of sunitinib for metastatic RCC. To reflect the patient population in Brazil, a second sample of patients who initiated first-line sunitinib on the 2/1 schedule will be collected and analyzed separately.

Primary Objectives:

1. Describe demographic and clinical characteristics of patients in Latin America diagnosed with metastatic RCC who received first-line sunitinib and switched from the 4/2 to the 2/1 schedule.
2. Characterize detailed first-line sunitinib treatment patterns, including dose, schedule, total duration of sunitinib treatment, duration on the 4/2 schedule, duration on the 2/1 schedule, reasons for stopping treatment lines, and supportive care.

Secondary Objectives:

1. Explore clinical outcomes after switching to the 2/1 schedule, including response to treatment, AEs, progression-free survival (PFS), and overall survival.
2. Describe demographic, clinical and treatment characteristics (eg, duration of treatment, reasons for stopping treatment), and clinical outcomes (eg, treatment response, AEs, PFS, and overall survival) among patients in Brazil who initiated first-line sunitinib treatment for metastatic RCC on the 2/1 schedule.

Study Design: Noninterventional, retrospective medical record review of patients with metastatic RCC who received first-line treatment with sunitinib and switched from the 4/2 to 2/1 administration schedule. A second sample of patients who initiated first-line treatment with sunitinib on the 2/1 schedule in Brazil will be collected and analyzed separately.

Population: Patients diagnosed with metastatic RCC with clear cell histology who switched from a 4/2 schedule to a 2/1 schedule of sunitinib in first-line metastatic treatment between January 1, 2014 and June 30, 2018. Patients must be aged 18 years or older at the time of the switch. The final dates defining this selection period will be dependent on country-specific ethics and reporting requirements. A second sample of adults who initiated first-line treatment with sunitinib on the 2/1 between January 1, 2014 and June 30, 2018 in Brazil will be collected and analyzed separately.

Variables: Patient characteristics, clinical characteristics, first-line treatment patterns, treatment-related outcomes, AEs, and survival.

Data Sources: Information will be abstracted from patients' medical records and compiled into an anonymized analytic database. All abstracted information will be retrospective.

Study Size: Data will be abstracted from a target of at least 150 medical records of patients treated at various sites across 7 Latin American countries.

[figure not shown]
Data Analysis: Analyses will include a descriptive summary of patient characteristics, first-line treatment patterns (eg, time to switch from 4/2 to 2/1; 4/2, 4/1, and total treatment durations), first-line disease progression from the start of 4/2 and the start of 2/1 schedules, AEs, and survival from the start of 4/2 and the start of 2/1 schedules. Time-to-event outcomes (ie, overall survival, treatment duration, PFS) will be described using the Kaplan-Meier method. Patients who initiated treatment on the 2/1 schedule will be analyzed separately from patients who switched from the 4/2 to 2/1 schedule.

Milestones: Key milestones include finalization of the protocol and case report form (quarter [Q]2 2019), initiation of site feasibility assessments (Q1 2019), initiation of the ethics review process (Q2 2019), start of data collection (to be determined; following completion of ethics review on a site-by-site basis), final interim analysis (Q3/Q4 2019), and final analytic results and final study report (to be determined based on site contracting timelines).

4. AMENDMENTS AND UPDATES

None.

PFIZER CONFIDENTIAL

[figure not shown]

5. MILESTONES

Milestone	Planned date
Initiate feasibility assessment with sites after sites complete the confidentiality agreement with PPD	Q1 2019
Finalize study materials	Q2 2019
Initiate ethics review process after PPD contracts with a participating site	Q2 2019
Start of data collection	TBD (following completion of ethics review on a site-by-site basis)
Final interim analysis	Q3/Q4 2019
Final analytic results	TBD (based on site contracting timelines)
Final study report	TBD (based on site contracting timelines)

TBD = to be determined; Q = quarter; PPD

PFIZER CONFIDENTIAL

6. RATIONALE AND BACKGROUND

Worldwide, kidney cancer is the ninth most commonly diagnosed cancer, with approximately 338,000 new cases diagnosed in 2012.¹⁰ In Latin America and the Caribbean, the incidence of kidney cancer is 2.5 and 4.7 per 100,000 females and males, respectively, which is slightly lower than the global incidence.¹¹ However, regional cancer registry data indicate a greater incidence per 100,000 in many Central and South American countries including Uruguay (females, 5.7; males, 13.4), Chile (females, 5.6; males, 10.4), Argentina (females, 4.5; males, 10.4), and Brazil (females, 3.0; males, 5.8).¹² Although kidney cancer also refers to cancers affecting the renal pelvis and ureter, which are typically transitional (urothelial) cell carcinomas, renal cell carcinoma (RCC) makes up approximately 80% of all kidney cancers.¹

RCC is a highly vascularized solid tumor and angiogenesis is linked to proliferation and propensity for metastasis.¹³⁻¹⁵ Over the past decade, targeted therapies, specifically angiogenesis inhibitors, have yielded significant improvement in the clinical outcomes of patients with metastatic RCC, leading to international guidelines for standard first-line treatment with sunitinib, bevacizumab + interferon, or pazopanib for patients with good or intermediate prognoses.¹

The standard administration schedule for sunitinib as first-line treatment for metastatic RCC is 50 mg per day (oral dose) for 4 weeks followed by 2 weeks off (ie, a 4/2 schedule). In this scheme, sunitinib demonstrated a greater median overall survival over interferon alpha (26.4 vs. 21.8 months, respectively; hazard ratio [HR] = 0.821; 95% confidence interval [CI], 0.673 to 1.001; $P = 0.051$).¹⁶ Median progression-free survival (PFS) was significantly longer in the sunitinib group (11 months) compared with the interferon alpha group (5 months) ($P < 0.001$). Yet, sunitinib-related Grade 3 adverse events (AEs) such as hypertension (12%), fatigue (11%), diarrhea (9%), and hand-foot syndrome (9%) were observed. The dose intensity of sunitinib must be maintained for disease control. Higher exposure has been linked to better treatment response, extended time to progression, and overall survival.¹⁷ However, treatment-related adverse events can lead to reductions in dose or dose interruptions, which in turn may lead to impaired quality of life and poorer outcomes as dosing is not maintained.^{17,18} The optimal treatment approach for maintaining sunitinib dosing while mitigating adverse events is unknown.²

Recent studies suggest that a schedule modified to 2 weeks of sunitinib followed by 1 week off (ie, a 2/1 schedule) improves tolerability with comparable outcomes.²⁻⁵ A change to the schedule may result in fewer Grade 3 or Grade 4 toxicities and increased treatment duration.⁵⁻⁸ In the RAINBOW study, researchers evaluated safety and efficacy of the 2/1 schedule among patients receiving sunitinib for metastatic RCC in multiple centers in Europe. Findings indicated patients who switched from the 4/2 to the 2/1 schedule experienced a favorable safety profile compared to the prevalence and frequency of adverse events occurring during the initial 4/2 schedule.⁷ A single site study of patients receiving first-line sunitinib also observed fewer toxicities among patients on the 2/1 schedule compared to those on the 4/2 schedule and comparable objective response rates and overall survival between the 2 groups.³ The STAR-TOR study, a large German registry containing patients who receive sunitinib for

metastatic RCC (among other patients), reported similar adverse event mitigation with the 2/1 schedule and treatment duration more than three times longer than those who received the 4/2 schedule.⁶ Longer duration translates to longer dose maintenance, which improves clinical outcomes.

Despite the potential benefit from a modified treatment schedule evidenced in studies among patients in the United States and Europe, real-world clinical outcomes among patients receiving the 2/1 schedule for metastatic RCC in Latin America are unexplored.^{5,9} Further research on current, real-world clinical outcomes in this population may assist in providing additional context on the types of patients who may benefit from this alternative schedule.

The aim of the present study is to describe clinical characteristics, treatment patterns, and clinical outcomes (eg, PFS, change in prevalence of AEs) of adult patients with metastatic RCC in Latin America who received first-line sunitinib on the 4/2 schedule and then switched to the 2/1 schedule. In Brazil, feasibility assessments indicate many physicians start patients on the 2/1 schedule upon initiation of sunitinib for metastatic RCC. To reflect the patient population in Brazil, a second sample of patients who initiated first-line sunitinib on the 2/1 schedule will be collected and analyzed separately. As patient characteristics, prescribing patterns, health care systems, and access to care in community practice settings differ from highly controlled clinical trial environments, clinical outcomes (eg, treatment response, PFS, overall survival) in real-world patient populations may vary from published trials. As current research on health outcomes among patients who received sunitinib on a 2/1 schedule for metastatic RCC in these countries is absent, there is a lack in understanding as to whether the alternative treatment schedule is safe and effective in patients in Latin America.

Results from this study may aid in the following:

- Understanding characteristics of patients who switched from a 4/2 to a 2/1 sunitinib schedule or initiated the 2/1 schedule in Brazil, and the resulting clinical outcomes in the real-world setting.
- Describing the occurrence of AEs on the 4/2 and 2/1 schedules.
- Providing real-world, baseline measures of contemporary prescribing patterns and health outcomes to which future innovations in therapy could be compared.

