8. RESEARCH METHODS

[figure not shown]
To achieve the study objectives described in Section 7, PPD, a research consultancy specializing in conducting multinational real-world health economic and outcomes studies, will analyze retrospective medical record data from 150 patients who received care at treatment centers across 7 Latin American countries. Prior to initiation of data collection activities, PPD, in consultation with Pfizer Inc. (Pfizer), will develop a customized case report form (CRF) to capture detailed data on demographics, clinical characteristics, treatment patterns, AEs, and health outcomes from eligible patients' medical records. The length of the CRF will be consistent with an abstraction time burden of approximately 30 to 45 minutes. After selection of potential sites by Pfizer, PPD will work with the sites to assess feasibility of the site's participation by using a site information form. If the study is determined to be feasible at a specific site, the principal investigator (PI) and their designated research team at the participating site will obtain the necessary ethics approvals for conducting this study. In countries where national ethics activities are required, a lead site in the relevant country will be selected to support the national

submission. Specific responsibilities to be conducted and coordinated by Pfizer, PPD, and individual sites during the site identification, feasibility assessment, contracting process, and data collection are shown in Figure 1.

Following receipt of the required ethics approvals, the site PI and/or designated research team will be provided a link(s) to the secure electronic CRF (eCRF) to enter the abstracted data electronically. The PI may personally abstract data and/or designate their research team to abstract data. Once a potential medical record is identified, the abstractor will answer multiple screening questions in the eCRF to confirm the selected medical record is eligible for inclusion. Next, the abstractor will complete the eCRF by retrospectively reviewing all available data in the patient's medical record.

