8.2.1. Patient Inclusion Criteria

1. Diagnosed with metastatic RCC with clear cell histology:
 - a. The patient may have been initially diagnosed with Stage IV or initially diagnosed at an earlier stage and progressed to having disease at distant sites (ie, metastatic disease).
2. Initiated first-line treatment for metastatic RCC with sunitinib on the 4/2 schedule (all countries) or initiated first-line treatment for metastatic RCC with sunitinib on the 2/1 schedule (Brazil only).
3. Switched to the 2/1 schedule (all countries) or initiated the 2/1 schedule (Brazil only) during the first treatment line between January 1, 2014, and June 30, 2018:
 - a. The final dates defining this selection period will be dependent on country-specific ethics and reporting requirements.
4. Aged 18 years or older at the time of the switch to the 2/1 schedule (all countries) or initiation of the 2/1 schedule (Brazil only).

PFIZER CONFIDENTIAL

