8.3. Variables

All measures/variables will be gathered from existing medical records using the eCRF. In the following sections, we describe the key analysis variables and study measures that will be gathered directly through the eCRF or constructed during analysis.

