8.7. Data Analysis

All measures described in [Section 8.3](#) will be summarized descriptively through the tabular and graphical display of mean values, medians, ranges, and standard deviations of continuous variables of interest and frequency distributions for categorical variables. Time-to-event outcomes (ie, overall survival, PFS, time to second-line initiation) will be described using the Kaplan-Meier method. All analyses will be conducted using SAS (version 9.4 or later) statistical software. Samples of patients who switched from the 4/2 to the 2/1 schedule from each country will be pooled and analyzed in aggregate. The sample of patients from Brazil who initiated first-line sunitinib on the 2/1 schedule will be analyzed separately. Results may be described for up to 2 subgroups that will be determined after the initial review of the data (eg, number of cycle on the 4/2 schedule).

As this study is descriptive and designed to generate hypotheses, direct comparisons between outcomes on the 4/2 schedule and on the 2/1 schedule will not be conducted. Potential confounders, such as characteristics that prompt the switch and other possible time-dependent factors (eg, dose modifications and delays), are not comprehensively collected or controlled for in this study design. Variability in timing of the switch from a 4/2 to a 2/1 schedule will affect the distribution of time-dependent outcomes after the switch (even in the absence of immortal-time bias), as some patients may switch “early” in their first-line therapy and others may switch “later.” Thus, causal inferences about the benefit of switching treatment schedules cannot be drawn.

PFIZER CONFIDENTIAL

Detailed methodology for summary and statistical analyses of data collected in this study will be documented in a statistical analysis plan, which will be dated, filed and maintained by the sponsor. The statistical analysis plan may modify the plans outlined in the protocol; any major modifications of primary endpoint definitions or their analyses would be reflected in a protocol amendment.

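### AEs are wanted by schedule and after the switch, but the listed variables give no onset or schedule at onset, and frequencies alone would mix AE rate with time on schedule

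*Combined protocol and SAP*

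**What the plan says.** **Aims.** Section 6 sets out to describe "clinical outcomes (eg, PFS, change in prevalence of AEs) of adult patients with metastatic RCC in Latin America" who moved from 4/2 to 2/1. It also names a description of AEs on both schedules as one use of the results. Section 7 makes outcomes after the switch, AEs included, a secondary objective.

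**Variables.** Section 8.3 opens by saying that "we describe the key analysis variables and study measures that will be gathered directly through the eCRF or constructed during analysis". Section 8.3.4 then has treatment-related AEs documented across first-line sunitinib as a whole. The only event dates it lists are progression and death. Section 8.3.3 is more specific on other matters: best response is taken separately on each schedule, and dates are listed for the start and stop of 4/2, the switch to and stop of 2/1, later schedule changes and dose changes. The note to Figure 2 in section 8.1 allows a gap between the two schedules.

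**Analysis.** Section 8.7 gives categorical measures "frequency distributions for categorical variables" and keeps Kaplan-Meier for overall survival, PFS and time to second line. It names no patient-time rate or common window for AEs. It also says that "direct comparisons between outcomes on the 4/2 schedule and on the 2/1 schedule will not be conducted".

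**Still to come.** Section 8 describes a CRF, yet to be developed, that will "capture detailed data on demographics, clinical characteristics, treatment patterns, AEs, and health outcomes". Section 8.7 leaves detailed methods to a separate SAP.

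**The concern.** To describe AEs after the switch, or AEs on each schedule, every AE must be placed before the switch, in the gap, on 2/1, or after a later schedule change. Nothing listed in 8.3.4 allows that. The omission is specific to AEs, since response and treatment are listed by schedule.

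A second problem follows if AEs are tabulated by schedule with frequencies alone. The share of patients with at least one AE rises with time observed, so two columns with different exposure differ even when the AE rate is the same. Section 6 invites the comparison in two ways. It speaks of a change, and it reports a European multicentre study in which switchers had a "favorable safety profile compared to the prevalence and frequency of adverse events occurring during the initial 4/2 schedule".

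At stake is a secondary objective; the primary objectives are unaffected. Timing matters because section 8.6.7 gives neither the sponsor nor the research consultancy access to medical records. A field left off the form could be recovered only by returning to the sites.

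**Working it through.** The plan states no AE rate, per-schedule duration or AE precision, so there is no figure to reproduce. The check has a textual part and an illustration.

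**1. Aim against listed variables**

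| Need | Listed? |
|---|---|
| Time on 4/2 and on 2/1 | Yes, 8.3.3 |
| Later schedule changes | Yes, 8.3.3 |
| Response by schedule | Yes, 8.3.3 |
| AE occurrence in first line | Yes, 8.3.4 |
| AE onset, or schedule at onset | No |
| AE ongoing at the switch | No |

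Section 10 mentions onset dates, possibly month and year only, for the safety report form. That form covers AEs explicitly attributed to a sponsor drug and certain exposure scenarios, and it is not described as an analysis source.

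**2. How far frequencies depend on time on schedule**

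Assumptions: a constant AE rate r per patient-month, the same on both schedules, with time on schedule not itself determined by AEs. With fixed time t, the share with at least one AE is 1 − exp(−r·t). With exponentially distributed time of mean t, it is r·t/(1 + r·t).

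For r = 0.10:
- Fixed, 3 months: 1 − exp(−0.3) = 26%. Fixed, 9 months: 1 − exp(−0.9) = 59%.
- Exponential, mean 3 months: 0.3/1.3 = 23%. Exponential, mean 9 months: 0.9/1.9 = 47%.

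| Months on 4/2, 2/1 | r = 0.10, fixed | r = 0.10, exponential | r = 0.05, fixed |
|---|---|---|---|
| 3, 9 | 26% v 59% | 23% v 47% | 14% v 36% |
| 9, 3 | 59% v 26% | 47% v 23% | 36% v 14% |

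At r = 0.10 the rate is 10.0 per 100 patient-months on both schedules throughout. This is by construction, because a constant hazard is assumed.

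If 2/1 truly halved a rate of 0.10, fixed times of 3 and 9 months give 26% versus 1 − exp(−0.45) = 36%. That looks like an increase, while the rates would be 10.0 and 5.0.

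**3. The same point with figures quoted in section 6**

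Take the 12% for Grade 3 hypertension on 4/2 and a duration ratio of 3, from the registry reporting "treatment duration more than three times longer than those who received the 4/2 schedule". With equal rates the 2/1 figure would be 1 − (1 − 0.12)^3 = 31.9%. With half the time on 2/1 it would be 1 − (1 − 0.12)^0.5 = 6.2%. Neither input describes these switchers. The 12% comes from a trial on the standard schedule, and the registry ratio is not a within-patient figure. Section 7, by contrast, expects follow-up after the switch to be limited. The direction of any imbalance is therefore open.

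**4. What a rate would not cure**

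Eligibility requires that the patient "Switched to the 2/1 schedule (all countries) or initiated the 2/1 schedule (Brazil only) during the first treatment line", so in the switch sample AEs on 4/2 come only from patients who later switched. Let f be the share of switches triggered by an AE, x the monthly rate of leaving 4/2 without switching for other reasons, and q the share of AEs that end sunitinib without a switch. Under constant rates, the 4/2 AE rate among switchers is r − q·r·(1 − f) + f·x. With r = 0.10 and f = 0.5 (assumed):
- q = 0, x = 0: 10.0 per 100 patient-months.
- q = 0, x = 0.03: 0.10 + 0.5 × 0.03 = 0.115, or 11.5.
- q = 0.3, x = 0: 0.10 − 0.3 × 0.10 × 0.5 = 0.085, or 8.5.

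Selection can push the 4/2 rate either way.

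**The case against.** **The detail may simply be elsewhere.** Section 8.3 lists key variables, section 8 promises a CRF with detailed AE data, and a SAP was to follow. A reader might infer that AEs cannot be placed relative to the switch at all. The documents do not support that: the CRF may capture onset. What stands is that the protocol's own list does not include it. A SAP cannot analyse a field that was never abstracted, and the abstract plans protocol and CRF finalisation for the same quarter, so the protocol list is the natural specification for the form.

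**No crude by-schedule table is promised.** This is correct. A reader might infer that the plan commits to AE percentages by schedule without exposure. It does not; it states only a general frequency summary and names nothing better for AEs.

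**The limitations are already disclosed.** Sections 8.7 and 8.9 say that factors prompting the switch and dose changes are uncontrolled, that timing of the switch affects later outcomes, and that causal inference is barred. This covers much of the selection issue in general terms. It does not mention AE time at risk, and a bar on inference does not assign an AE to a schedule.

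**The illustration rests on a simple model.** It does. In the extreme where every AE ends 4/2 treatment, the percentage of switchers with an AE on 4/2 equals f whatever the time on 4/2. The column would then reflect why patients switched, which is still not a clean measure of tolerability. Also, 4/2 always comes first, so if AE risk changes with time on drug, patient-month rates would differ with no schedule effect.

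**The wording on change is only an example in the rationale.** This is true, and section 7 does not repeat it. It still conflicts with 8.7.

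**Conclusion.** The point holds as a gap in the protocol. The aims in sections 6 and 7 need AEs by schedule, and the variables listed in 8.3.4 do not provide it. The one summary in 8.7 that fits AEs would, if shown by schedule, generally mix AE rate with time on schedule. The section 6 phrase about change should be reconciled with 8.7.

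The size is illustrative only. With an equal constant rate of 0.10 per month and 3 versus 9 months, the figures are 26% versus 59% (fixed exposure) or 23% versus 47% (exponential exposure), and the reverse if the durations are reversed. All inputs are assumed.

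A reader might go on to infer that the results will favour one schedule, or that exposure-adjusted rates would make the schedules comparable. The documents support neither: the direction of the duration imbalance and of the selection effect is unknown, and rates do not remove order or selection. This is a cheap improvement, best made before abstraction starts.

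**What to change.** 1. **Section 8.3.4.** For each AE record the schedule in force at onset (4/2, gap, 2/1, later schedule), the onset date where available, and whether the AE was ongoing at the switch. Month and year alone are not enough, because they cannot place an AE that began in the switch month.
2. **Section 8.7.** Beside the frequencies, report for each schedule the patients affected, patient-months (from the dates already listed in 8.3.3) and new-onset events per 100 patient-months. Show AEs ongoing at the switch in a separate row. Label the table descriptive and not for comparison.
3. **Section 6.** Replace the reference to a change in AE prevalence with wording such as AEs recorded on each schedule.
4. **Section 8.9, optional.** State that AE time at risk differs by schedule, that 4/2 always comes first so rates may differ if AE risk changes with time on drug, and that 4/2 AEs come only from patients who later switched, with unknown direction of effect.

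The cost is one or two eCRF fields per AE within a form planned at 30 to 45 minutes, and some incomplete chart data. Parallel columns may themselves invite comparison, which is why the label is needed. No hypothesis test or subgroup is added.
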